We will enroll menthol (n = 125) and non-menthol (n = 125) YA smokers who initiated regular smoking in the past 12-months or who initiated regular smoking more than 12 months ago, and measure appeal/reinforcement for menthol and non-menthol cigarettes and the impact of appeal/reinforcement on changes in smoking (progression, nicotine dependence, and cigarette harm perceptions) at a 6-month follow-up. Appeal/reinforcement will be assessed via two complementary measurement paradigms: one in the laboratory using a well-validated behavioral economic choice task and the other in the natural environment using ecological momentary assessment (EMA). Laboratory studies provide a great deal of efficiency and internal control, allowing for causal inference of acute subjective response; while EMA allows for similar causal sequencing of behavior, but in an ecologically valid format in the smoker's natural environment. It is hypothesized that, compared to nonmenthol smokers, menthol smokers will show greater appeal/reinforcement, both in the laboratory and via EMA, and will be more likely to show progression to regular smoking, increases in nicotine dependence, and lower cigarette harm perceptions by a 6-month follow-up. The association between menthol preference and smoking outcomes will be reduced or non-significant after including measures of appeal/reinforcement in the model; suggesting that menthol's appeal/reinforcement accounts for smoking progression. This research will isolate the unique effects of menthol in smoking and will help inform regulatory decisions about the abuse liability of menthol cigarettes and the use of flavors in other tobacco products in future studies.

Specific Aims

Aim 1 (Phase 1): Examine the absolute and relative reinforcing value (appeal) of menthol vs. non-menthol cigarettes using a validated laboratory-based behavioral economic choice task.

Aim 2 (Phase 2): Examine the subjective effects (appeal) of menthol vs. non-menthol cigarettes (own brand) during 14 days of ecological momentary assessment (EMA) in the natural environment.

Aim 3 (Phase 3): Examine the degree to which laboratory (Phase 1) and EMA (Phase 2) measurements of menthol appeal/appeal causally impact (i.e., mediate) the association between menthol brand preference at baseline and 6-month smoking outcomes (progression, increased nicotine dependence, lower cigarette harm perceptions).

Study Design

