In addition to the aforementioned recruitment methods, we will use BuildClinical, who will assist with recruitment by designing and managing targeted, GCP-compliant, IRB approved advertising. **BuildClinical** is a data-driven software platform that helps academic researchers recruit participants for research studies more efficiently using social media, software, and machine learning. BuildClinical utilizes study-specific advertisements to engage participants on digital platforms such as Facebook, Google, WebMD, etc., and redirect them to a study-specific landing page should they click it. On the landing page, the person can complete an online pre-screen questionnaire that gets routed into BuildClinical's platform. BuildClinical's Secure Socket Layer (SSL) software, which encrypts all inputted information, keeps participant information private and HIPAA compliant. BuildClinical's backend servers are stored in the USA at some of the most secure data centers in the world. The study team will access BuildClinical's platform to review and select qualified screening participants for additional screening. Interested individuals may then choose to enroll in the study by completing Informed Consent and HIPPA prior to scheduling a baseline lab or virtual session.

We have included the BuildClinical advertisement materials, pre-screening questionnaire, and study information landing page design and

IRB NUMBER: 10581
B NUMBER: 10581
IRB APPROVAL DATE: 02/14/2022
PROVAL DATE: 09/13/202112

content.[Inclusion/Exclusion criteria](#)

Inclusion criteria:

- (1) Ages 18 to 26;
- (2) Currently smoke cigarettes "somedays" or "everyday";
- (3) Started smoking "somedays" or "everyday" in the past 12-months or more than 12 months ago.
- (4) A strong preference for menthol or non-menthol cigarettes (i.e., smoke one type $\geq 80\%$ of the time).
- (5) Able to read and understand the informed consent
- (6) Willingness to abstain from nicotine containing products or other combustible products (e.g., smoked cannabis) for at least 12 hours prior to each in-person or virtual laboratory visit (confirmed by CO $\leq 8\text{ppm}$ for each in-person study visit in Phase 1). Will be rescheduled once if CO is not within acceptable range.

Exclusion criteria:

- (1) Current use of nicotine replacement therapy (NRT);
- (2) Currently pregnant or planning to become pregnant, or breast feeding (verified by pregnancy test at each study visit/session);

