- (3) Participant self-reports a diagnosis of lung disease, including asthma, cystic fibrosis, or chronic obstructive pulmonary disease; PI.
- (4) History of cardiac event or distress within the past 3-months

Individuals will be provided referrals for treatment at the completion of the study. Men and women of any ethnic or racial group are eligible to participate in the study if they meet inclusion/exclusion criteria.

Update about the impact of Tobacco 21 regulation on study recruitment

Because of the new Tobacco 21 regulations at the state and federal level, individuals under the age of 21 are not allowed to purchase tobacco products, and the research team is no longer allowed to "furnish" tobacco products to individuals under the age of 21 without a research waiver. The Governor of Oklahoma signed SB319 into law on April 22, 2021 which provides an exemption for scientific study from penalties for furnishing tobacco products to persons under the age of 21 years. SB319 is scheduled to take effect on November 1st, 2021. On this date, the research team will begin recruiting persons aged 18-20 years for full participation in the research study.

Informed Consent Process

Participants will provide verbal or electronic consent to be screened over the phone or online, respectively. Verbal consent will be obtained for participants completing the telephone screener. Prior to beginning the telephone screener, participants will be told (a) their research data provided on the telephone screen will be confidential and coded only with a unique identifier; (b) their personally identifiable information will be kept separate from their research data on a password protected server

that can be accessed only by approved study personnel; and (c) there is a possible risk of loss of confidentiality although the risk is considered low given that research data will be de-identified.

If recruited during university normal operating procedures (when in-person data collection is allowed), eligible participants will provide written consent in person immediately before their first laboratory visit begins. This will take place in our lab. We will go over every section of the consent document with the participant, then ask if he or she has any other questions before signing. Each participant will be allowed time to read the consent document and ask questions before any data are collected. A copy of the consent form will be given to the participant.

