A 2 (menthol preference) X 2 cigarette type (usual brand versus experimental brand) mixed ANOVA will be conducted to examine main effects and interactions on the outcomes of interest. Models will examine cigarettes per day (CPD), nicotine dependence, race/ethnicity, gender, and age of smoking onset as potential covariates. Factors related to Phase 1 drop-out will be examined as potential covariates. If nicotine and CPD are collinear, the most significant predictor of the outcome will be retained in the model. Significant interactions will be followed up with individual contrasts of cell means using Fisher’s Least Significant Difference tests. In exploratory analyses, a 2 (menthol preference) X 4 (race/ethnicity: White, Black, Other, Hispanic) between-subjects ANOVA and a 2 (menthol preference) x 2 (gender) between subject ANOVA will be conducted separately for the BL Visit to evaluate differential reactions to own brand cigarette smoking by race/ethnicity and by gender. Comparison of own brand/usual brand and experimental cigarette ratings will also be made to determine the perceived similarity of the experimental cigarette to one’s own brand and as a function of gender and race/ethnicity. NOTE: We expect that ratings of appeal/reinforcement for the experimental cigarettes will be lower than ratings of appeal for usual brand. Ratings of experimental cigarettes will be examined as a potential covariate in Aim 3 models. Age of smoking initiation will also be examined as a potential covariate. Covariates with $p < .05$ will be retained in final models.

Phase 2/Aim 2 Analyses

Primary Outcomes: (a) within-day subjective response (craving reduction, satisfaction, psychological reward, physical sensations like throat grab) to the most recent cigarette smoked (menthol vs non-menthol); (b) betweenday subjective response.

Secondary Outcomes: (a) Aggregate ratings of subjective response (over the course of 14 days) by baseline menthol brand preference (at the person-level, rather than by day); (b) changes over the course of days (creating an average change score for each person); (c) within-person variability by calculating the standard deviation of daily cigarette reward, satisfaction, craving reduction, and throat hit ratings for each person; (d) cigarettes per day (within-day, over days); and (e) craving intensity (within-day, over days).

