Participants will not be exposed to any more risk than the usual risk they expose themselves to by choosing to smoke. Questionnaires and carbon monoxide measurement are all non-invasive and involve minimal risk to study participants. According to new statute passed in early 2020, tobacco products, including Camel Crush cigarettes, are available in convenience stores to persons 21 years of age and older. Potential risks to participants include: 1) risk of using cigarettes, 2) loss of confidentiality or privacy, and 3) potential discomfort from being asked to abstain from nicotine. Participants who are under the age of 21 are still eligible to participate in the study, but will complete a modified version of the study protocol. They will complete the usual smoking session (e.g., lab session 1), the EMA, and follow-ups, but they will not be given experimental cigarettes until or unless we have approval to do so from the authorities. The PI is working with the OUHSC Office of Legal Counsel to obtain a waiver from the Oklahoma Attorney General that would allow us to provide cigarettes to individuals under the age of 21 for research purposes. Once we have approval, the IRB will be notified and we will proceed with sessions 2 and 3 and of the proposed study with individuals ages 18 to 20.

The laboratory where visits will be completed was constructed with a special ventilation system for quickly removing smoke from the experimental rooms to reduce excess smoke exposure to participants and researchers. Smoking cessation resources will be available to all participants at completion of the study, or earlier if requested, and participants will be provided with a list of cessation resources including the Oklahoma Helpline, a free, 24/7, telephone-based resource to provide tobacco cessation counseling.

Protection Against Risks

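### The protocol gives two rules for whether 18-20-year-olds complete Visits 2 and 3, and the Phase 1 mixed ANOVA has no stated way to use participants who have Visit 1 but not Visit 2

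*Combined protocol and SAP*

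**What the plan says.** **Who does Visits 2 and 3.** The section on the impact of Tobacco 21 regulation reports a state exemption: "SB319 is scheduled to take effect on November 1st, 2021". It continues: "On this date, the research team will begin recruiting persons aged 18-20 years for full participation in the research study". Human Subjects Protection, Potential Risks, says of under-21s: "They will complete the usual smoking session (e.g., lab session 1), the EMA, and follow-ups, but they will not be given experimental cigarettes". This limit lasts while approval is outstanding. The approval named there is a different one, since the investigator is working to "obtain a waiver from the Oklahoma Attorney General that would allow us to provide cigarettes to individuals under the age of 21". The section then says: "Once we have approval, the IRB will be notified and we will proceed with sessions 2 and 3", for ages 18 to 20. It does not mention the statute. The text carries the stamp "IRB APPROVAL DATE: 02/14/2022", and an older stamp of 09/13/2021 also remains.

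**How Phase 1 is analysed.** Phase 1/Aim 1 Analyses names one main model: "A 2 (menthol preference) X 2 cigarette type (usual brand versus experimental brand) mixed ANOVA will be conducted to examine main effects and interactions". The Phase 1 design section makes cigarette type a within-subjects factor. Usual-brand ratings come from Visit 1. Study Products and the Visit 2 description place the experimental cigarette at Visit 2. The only Phase 1 provision for incomplete data is that factors related to drop-out are examined as possible covariates. Multiple imputation is named under Phase 2/Aim 2.

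**Planned size.** "We will enroll menthol (n = 125) and non-menthol (n = 125) YA smokers". The documents give no power calculation and no expected number of under-21s.

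**The concern.** Staff cannot tell from the current text which visits an 18-20-year-old should be offered, or from what date. The age range is 18 to 26, so this affects part of the eligible population.

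The statistical consequence concerns anyone who has the usual-brand cell and lacks the experimental cell. A classical mixed ANOVA needs both cells per person, so it sets aside a Visit 1 rating that was collected. Where the cause is the age rule, the loss depends on age and is not a random thinning of the sample. Current age is not among the Phase 1 covariates; the list has age of smoking onset.

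There is a related risk in Aim 3. Mediation is read from the fall in the menthol coefficient when the appeal measure enters at Step 3. The elasticity measure comes from Visit 2 and the breakpoint from Visit 3. If Step 2 is fitted on everyone and Step 3 only on those with the mediator, part of any change in the coefficient may come from the change of sample.

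**Working it through.** **1. The two sections side by side.**

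| | Tobacco 21 update | Potential Risks |
|---|---|---|
| Visits for ages 18-20 | Full participation | Session 1, EMA and follow-ups while approval is pending |
| Legal route | State statute (SB319) | Attorney General waiver, then notice to the IRB |
| Effective from | 1 November 2021 | Date of an approval not yet given |
| Under-21s already enrolled | Not addressed | Not addressed expressly; sessions 2 and 3 to proceed for ages 18 to 20 |

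The later stamp, 14 February 2022, falls after the statute's effective date, so both rules stand in the text at a time when only one can apply. The Potential Risks text is conditional and looks un-updated. The statute could be the approval it awaits, but neither section says so.

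**2. What a standard fit does.** In a simulated data set of 250 people with a 20% chance of lacking the experimental cell, 54 lacked it. The repeated-measures ANOVA routine rejected the data as unbalanced. A classical fit therefore has to be restricted to 250 - 54 = 196 people. A linear mixed model with a random participant intercept used all 250 people and all 250 + 196 = 446 observations.

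**3. Possible cost to the Visit 1 menthol contrast.** The plan has no power figure to reproduce. Inputs:
- 125 per group, from the Study Objective.
- Share f lost from each group: assumed, 10-30%.
- Standardised difference d = 0.35 and two-sided alpha 0.05: assumed.

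Formulas:
- n per group = 125(1 - f)
- SE ratio = sqrt(1/(1 - f))
- Power ≈ Φ(d/sqrt(2/n) - 1.96)

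| f | n per group | People lost of 250 | SE ratio | d/sqrt(2/n) | Power |
|---|---|---|---|---|---|
| 0 | 125 | 0 | 1.000 | 2.77 | 79% |
| 10% | 112.5 | 25 | 1.054 | 2.63 | 75% |
| 20% | 100 | 50 | 1.118 | 2.47 | 70% |
| 30% | 87.5 | 75 | 1.195 | 2.31 | 64% |

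Using all Visit 1 data keeps the f = 0 row for this contrast, whatever happens at Visit 2.

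**4. Which Aim 3 mediators the age rule touches.** Under-21s on the modified protocol keep session 1, EMA and follow-up. Visit 1 ratings and EMA slopes are therefore still available. Only the breakpoint (Visit 3) and elasticity (Visit 2) are missing.

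**The case against.** The strongest reply is that this is an editorial lag. One section is headed as an update, the other is conditional, and together they read as a later and an earlier stage of the same process. That is probably right. It does not remove the need to reconcile them, because they name different legal routes and do not refer to each other.

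Three stronger readings are tempting, and the documents do not support them.

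- **That every under-21 enrolled before 1 November 2021 has Visit 1 only.** No section says this. Potential Risks foresees sessions 2 and 3 for ages 18 to 20 once approved and does not exclude people already enrolled. Study Design also provides for later contact with participants whose laboratory sessions were deferred because of COVID-19. A permanent Visit-1-only group could be small or empty.
- **That the plan discards Visit 1 data.** It does not order complete-case deletion. The absolute reinforcing value is defined as a between-subject difference at Visit 1, exploratory ANOVAs use the baseline visit alone, and Aim 3 models with Visit 1 or EMA measures can include these people. The imputation sentence under Aim 2 might be meant more widely, though nothing says so. What stands is narrower: the one main Phase 1 model named drops these people in a standard fit, and no rule is given for them.
- **That a third of the sample is lost, because ages 18-20 are 3 of the 9 eligible years.** That needs even enrolment by age and the restriction to last for the whole study. The Tobacco 21 update contradicts the second condition.

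It is also fair to say that the Aim 3 section does not state that the steps use different samples. It leaves this open.

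**Conclusion.** The point holds as an inconsistency to reconcile and an inexpensive improvement to the analysis. It is not a demonstrated loss of data. The two sections give different rules for 18-20-year-olds in the same text, and the handling of participants with Visit 1 but not Visit 2 is unspecified in the main Phase 1 model.

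The size is hypothetical because the documents do not give the number affected. With an assumed 10-30% affected equally in both groups, the standard error of the Visit 1 menthol contrast rises by about 5-20%. At a 20% share, power for d = 0.35 goes from about 79% to about 70%. The Aim 3 issue is conditional on the steps being fitted to different samples and, as far as the age rule goes, is confined to the breakpoint and elasticity mediators.

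**What to change.** 1. **Reconcile the two sections** into one rule with one legal basis and one effective date, and state whether under-21s enrolled before that date are called back for Visits 2 and 3. Which rule applies is for the investigator and the IRB to settle.
2. **Replace the 2x2 mixed ANOVA by a linear mixed model** (REML, random participant intercept) with menthol preference, cigarette type and their interaction, fitted to all available sessions. Include current age as a covariate, because missingness under this rule depends on age, and keep it in whatever its p-value, despite the plan's p < .05 retention rule. Take the absolute reinforcing value contrast from all Visit 1 data.
3. **In Aim 3, fit Steps 1-3 on the same participants for each mediator**, and report the number in each set.

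The cost is an edit to the protocol text and a change of procedure in the analysis plan, with no new data. There are two downsides. The mixed model assumes that the absent ratings are missing at random given age, menthol preference and the ratings observed. It also recovers information mainly for the usual-brand contrast, because people without the experimental cell cannot show a within-person difference. A common-sample Step 2 uses fewer people than are available, so its menthol coefficient is less precise.
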